DURATION OF PARTICIPANT PARTICIPATION AND DURATION OF STUDY	
Cohort 1: Participants will be on study for up to 45 days.
 
Screening: up to 14 days
 
Treatment: 1 day (participants to be admitted to the hospital during the day; no overnight stay)
 
Follow-up: 31 days after treatment dose day
 
Cohort 2: Participants will be randomized to either of two treatment arms, kansui or placebo, using a crossover design with a 56-day washout period in between treatment arms. Participants will be on study for up to 146 days.
 
Screening (for each arm): up to 14 days prior to treatment arm.
 
Treatment (for each arm): 3 days (participants to be admitted to the hospital each day; no overnight stays)
 
Follow-up (for each arm): 31 days after the initial dose for that treatment arm.
 
The total duration of the study is expected to be 1 year.

CONCOMMITANT MEDICATIONS	
Allowed:
 
 1. In the absence of drug-drug interaction information regarding kansui, participants may use their usual medications, as long as they are medically necessary and can be monitored safely during the study period. 
Prohibited:
 
 1. As stated in the exclusionary criteria above, participants may not have exposure to any immunomodulatory drug (including maraviroc) in the 16 weeks prior to study or during study period. 2. Also as stated in the exclusionary criteria, participants may not have prior or current use of experimental agents used with the intent to perturb the HIV-1 viral reservoir. 3. Participants may not be allowed to take anti-motility agents during the study period in order to accurately assess adverse events related to diarrhea. 4. Participants will not initiate new medications that may also cause diarrhea, including proton pump inhibitors, antibiotics, antidepressants, colchicine, digitalis, etc., during the study period. 
In addition to the above medications, per traditional Chinese medicine practices, participants should also not ingest ice-cold food or beverages, spicy foods, or seafood in the two days prior to, during, and up to two days after kansui treatment.

EFFICACY EVALUATIONS	
 • CD4+ and CD8+ T cell activation (expression of CD69, CD38, and HLA-DR). • Latent HIV reservoir quantification (cell-associated HIV RNA and plasma HIV RNA levels).

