Given that the purpose of studying kansui in this study is to evaluate whether it can reactivate HIV from latently infected cells, there is a risk that taking kansui for up to 3 days could lead to transient loss of viral suppression and subsequent development of resistance to the participant's current antiretroviral therapy. However, given the short duration of kansui administration and the predicted small increases in plasma viremia as a result of kansui, we believe that these risks will be low. Nonetheless, as per protocol with other currently studied latent reversing agents (LRAs), we will perform frequent plasma HIV RNA monitoring (screening, every dosing day, each 24-hour follow-up, and days 31 and 132) and even more frequent monitoring of the research-based reservoir measurements of cell-associated HIV DNA and RNA (see section 9.1 below). In addition, we will only enroll participants for whom alternative ART regimens are available in the event that their previously effective regimens are compromised. Finally kansui treatment will be discontinued if the participant has any two consecutive plasma HIV RNA levels levels >200 copies/mL, or any single plasma HIV RNA level >1000 copies/mL. These values would be above the levels predicted to be seen with HIV reactivation with most current latent reactivating agents and are safety stopping criteria currently used for other HIV latent reactivating agent trials, e.g., the AIDS Clinical Trials

Group (ACTG 5336) trial, evaluating the role of Sirolimus on immune activation and the latent reservoir in chronic HIV-infected, ART-suppressed individuals.

Reproductive risks

Given the unknown reproductive risks associated with kansui as tested scientifically, and its use in traditional Chinese medicine as an abortifacient,⁸ women of childbearing potential must have a negative serum pregnancy test in the medical workup for study entry and excluded from participation if pregnant. All participants must agree to use two forms of contraception throughout the study period and up to 90 days after the last dose of kansui (to account for the male sperm cycle). Women (or female partners of male study participants) must not breastfeed during the study period and up to 90 days after the last dose of kansui.

Confidentiality

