9 STUDY PROCEDURES AND GUIDELINES

Prior to conducting any study-related activities, written informed consent and the Health Insurance Portability and Accountability Act (HIPAA) authorization must be signed and dated by the participant.

Eligible participants will receive a single dose for either a single or 3 consecutive days (Cohort 1: day 1; Cohort 2: days 1, 2, 3). Extensive sampling will occur before, during, and after the last dose. A full schedule of events for each cohort is provided below:

Study Events Table Cohort 1

Parameter	Day -14 ^a	Day -7 ^a	Day 1	Day 1	Day 1	Day 1	Day 2	Day 31	Early Withdrawal Visit (if applicable)
	Screen	Baseline	0 hrs ^b	0.5 hrs ^b	2 hrs ^b	4 hrs ^b	24-hr post-dose Follow-up		
Informed consent	X								
Questionnaires	X	X	X				X	X	X
Demographics	X								
Medical history, medications, AE	X	X	X				X	X	X
Vital signs	X		X		X	X	X	X	X
Physical exam (either Complete / Targeted) ^c	X		X				X	X	X
Study kansui administration			X						
Complete blood count w/diff	X		X	X	X	X	X	X	X
Comprehensive Metabolic Panel	X		X				X	X	X
Quantiferon test (QFT)	X								X
Pregnancy test (female participants)	X							X	X
Thyroid-stimulating hormone (TSH)	X								
Hep B Ag	X								
HCV Ab	X								
CD4+/CD8+ T cell counts	X	X	X				X	X	X
HIV RNA: standard assay	X	X	X				X	X	X
Immune activation (CD69, CD38, HLA-DR)	X	X	X	X	X	X	X	X	X
HIV reservoir measures	X	X	X	X	X	X	X	X	X
PBMC and plasma cryopreservation for future studies (PK, transcriptome analyses)	X	X	X	X	X	X	X	X	X

^a Days -14, -7, 4 and 31 represent the time from receiving the first dose of Euphorbia kansui extract powder prepared as tea on the Day 1 Visit.

^b Hours 0, 0.5, 2, and 4 represent time from receiving Euphorbia kansui extract powder prepared as tea dose on that dosing day.

^c The complete physical exam must occur at Screening. In the event of an Early Withdrawal Visit a complete physical exam is to be performed. A targeted physical exam is to be completed for all other time points.

Cohort 2. Participants in cohort 2 will be randomly assigned to either *kansui* or placebo first. The study will include a 56-day washout period between the two treatments (*kansui* and placebo). On study Day 88 a “second screening” visit for the second treatment assignment will occur; the second treatment phase will begin on study Day 102 and end on Day 132.

Study Events Table Cohort 2 (Treatment Phase 1)

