10.2 Serious Adverse Experiences (SAE)

An SAE is defined as any AE occurring at any dose that results in any of the following outcomes:

- death
- a life-threatening adverse experience
- inpatient hospitalization or prolongation of existing hospitalization
- a persistent or significant disability/incapacity

- a congenital anomaly/birth defect

Other important medical events may also be considered an SAE when, based on appropriate medical judgment, they jeopardize the participant or require intervention to prevent one of the outcomes listed.

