10.2.1 Serious Adverse Experience Reporting

The study site will document all SAEs that occur (whether or not related to study drug) per the University of Utah IRB Guidelines. The collection period for all SAEs will begin after informed consent is obtained and end after procedures for the final study visit have been completed.

In accordance with the standard operating procedures and policies of the local Institutional Review Board (IRB), the site investigator will report SAEs to the IRB.

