11.3 Replacement of Participants

Participants who withdraw from the study treatment before last day of study drug dosing (i.e., Day 1 for Cohort 1, Day 104 for Cohort 2) will be replaced by another enrolled participant to maintain total study numbers.

The CRF will document the reason for the withdrawal and date of withdrawal. Date of withdrawal will be documented as the date of last study drug treatment, not the date that the decision to withdraw treatment was made.

Participants will be followed after withdrawal from the study for 3 calendar days after cessation of treatment. All adverse events during that period will be reported.

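### In Cohort 1 and in Cohort 2 participants who receive kansui second, SAE collection closes 28 to 30 days after the last kansui dose, leaving 60 to 62 days of the 90-day reproductive precaution period uncovered

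*Combined protocol and SAP*

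**What the plan says.** Section 2.1 (Reproductive risks) gives two grounds for caution: the reproductive risk of kansui is unknown, and traditional practice uses it to end pregnancy. It requires contraception during the study and "up to 90 days after the last dose of kansui (to account for the male sperm cycle". The next sentence applies the same 90 days to breastfeeding, for women in the study and for female partners of men in the study. Exclusion 14 in section 6.3 repeats the 90 days for contraception.

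Section 10.2.1 has SAE collection "begin after informed consent is obtained and end after procedures for the final study visit have been completed". Section 10.2 counts "a congenital anomaly/birth defect" among the SAE outcomes.

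The dosing days in section 9 are "Cohort 1: day 1; Cohort 2: days 1, 2, 3", and section 11.3 gives the last dosing day as "Day 1 for Cohort 1, Day 104 for Cohort 2". The Cohort 1 events table ends at Day 31; the synopsis words this as "Follow-up: 31 days after treatment dose day". For Cohort 2, section 9 states that "the second treatment phase will begin on study Day 102 and end on Day 132". No procedures take place in the washout, Days 32 to 87. Under section 11.3, a participant who withdraws from the study is followed for 3 calendar days after treatment stops.

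The events tables schedule pregnancy tests for female participants at screening, Day 31 and early withdrawal, and in Cohort 2 also at Days 88 and 132. Pregnancy is a discontinuation criterion in sections 10.4 and 11.1.

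**The concern.** The protocol asks participants to take precautions for 90 days because of a named risk, but for some of them it stops asking about events after roughly a third of that time. A pregnancy that began or came to light later, in a participant or a partner, would have no scheduled route into the trial record. A birth defect is a listed SAE, yet a pregnancy conceived after dosing could not reach term before Day 31 or Day 132, so this collection period cannot realistically record one.

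Safety is the primary objective. What is at stake is whether an exposed pregnancy would be noticed and followed.

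**Working it through.** **Check of the calendar.** The protocol's own durations reproduce from its visit days:
- Cohort 1: 14 + 31 = 45 days on study, as stated in section 4.1.
- Cohort 2: 14 + 132 = 146 days, as stated.
- Washout, Days 32 to 87: 87 − 32 + 1 = 56 days, as stated.

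Section 4.1 also gives Day 88 to Day 101 for the second treatment phase, but it too starts the second treatment on Day 102. Sections 8.1, 9 and 11.3 agree with that, so I use Days 102 to 104 for dosing.

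**Days covered.** Covered days = final visit day − last kansui dose day. Uncovered days = max(0, 90 − covered days).

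| Group | Last kansui dose | Final visit | Covered | Uncovered of 90 |
|---|---|---|---|---|
| Cohort 1 | Day 1 | Day 31 | 30 | 60 (66.7%) |
| Cohort 2, placebo first | Day 104 | Day 132 | 28 | 62 (68.9%) |
| Cohort 2, kansui first | Day 3 | Day 132 | 129 | 0 |

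If follow-up is read literally as 31 days after the dose, or after the initial dose of the period, the first two rows become 29 to 31 covered days, with 59 to 61 uncovered (65.6% to 67.8%). The reading makes little difference.

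**Whole trial.** Section 8.1 randomises treatment order with a random number generator and states neither blocking nor a split. Let k be the number of the six Cohort 2 participants who receive kansui first, and assume all complete.
- Participants affected = 2 + (6 − k).
- Uncovered person-days = 2 × 60 + (6 − k) × 62, out of 8 × 90 = 720.

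| k | Affected | Uncovered person-days | Share |
|---|---|---|---|
| 6 | 2 of 8 | 120 | 16.7% |
| 3 (assumed 3:3) | 5 of 8 | 306 | 42.5% |
| 0 | 8 of 8 | 492 | 68.3% |

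**Withdrawal.** A participant who leaves the study after a kansui dose is followed for 3 days, so 90 − 3 = 87 of 90 days (96.7%) are uncovered. This concerns withdrawal from the study: section 11.1 encourages those who only stop treatment to complete the remaining visits.

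**What is collected.** The scheduled tests cover female participants only. I found no procedure in the visible text for partner pregnancies, for following a pregnancy to outcome, or for any contact after the final visit.

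**The case against.** - **Two-thirds for everyone.** A reader might infer that two-thirds of the window is lost across the trial. The documents do not support that. Cohort 2 ends on Day 132 in either order, so kansui-first participants pass the 90-day limit (Day 93) while still in the study, with pregnancy tests at Days 31, 88 and 132. That coverage is in time only, since Days 32 to 87 have no procedures.
- **A contradiction.** A reader might see sections 2.1 and 10.2.1 as contradicting each other. They do not. The 90 days is a contraception and breastfeeding period, and the protocol never promises to observe participants throughout it. Treating it as an observation window is an inference, though a fair one from the reason section 2.1 gives.
- **All men affected.** A reader might infer that the gap reaches male participants whatever the eligibility rule means. Exclusion 14 opens by excluding participants of reproductive potential, without limiting this to women. Read literally, few or no participants are concerned. The same item then sets contraception rules for such participants, so the number concerned is unknown until it is reconciled.
- **A statistical cost.** The gap might be said to prevent a conclusion about reproductive safety. Full follow-up would not permit one either: with 0 events in 8, the one-sided 95% upper limit is 1 − 0.05^(1/8), about 31%. Nor does the 129 versus 28 days distort a planned comparison, since section 14.3 tabulates adverse events by cohort and not by sequence.
- **Provisions elsewhere.** Section 16.5 has the investigator report unanticipated problems involving risks to participants or others, which could reach a partner. SAE documentation follows IRB guidelines that are not in the documents, and the consent pages were removed before review. Either might ask for later pregnancies to be reported. The statement that none are collected therefore holds for the visible text only.

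What remains is that no visible provision sets a contact at or near 90 days for the affected groups.

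**Conclusion.** The gap is real for Cohort 1 and for Cohort 2 participants who receive kansui second. In those groups 67% to 69% of the protocol's precaution period falls after SAE collection closes, and more for anyone who withdraws from the study after kansui. It does not exist, in time, for kansui-first participants who complete.

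The group figures rest only on the protocol's visit days. The whole-trial figures rest on an assumed split and full completion, so the ranges should be quoted with them. How many people are concerned also depends on how exclusion 14 is resolved.

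This is a worthwhile, inexpensive improvement in safety follow-up. It leaves the planned analyses unaffected, and its value lies in detecting and tracing an exposed pregnancy.

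**What to change.** In sections 10.2.1 and 11.3, and as a line in the events tables of section 9, extend collection of pregnancies (participants and female partners) and related SAEs to the 90-day limit the protocol already states. One scheduled telephone contact is enough:
- Cohort 1: Day 1 + 90 = Day 91.
- Cohort 2: 90 days after the last dose of either treatment, which for completers is Day 104 + 90 = Day 194. Timing it from either treatment gives both sequences the same contact and does not reveal the order.
- Participants who withdraw: the same contact, counted from their last dose of either treatment.

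State that any reported pregnancy will be followed to outcome. The call alone would not capture a birth defect.

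Separately, reconcile the sentences of exclusion 14 with one another and with section 2.1. Which reading is right is for the investigators to decide.

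**Cost.** Protocol and consent wording, and one call per participant. Close-out moves by 91 − 31 = 60 days in Cohort 1 and 194 − 132 = 62 days in Cohort 2, for the safety contact only. Outcome follow-up is a separate, contingent cost: if a pregnancy is reported it may take months, and a partner's data need the partner's permission. No dose, treatment rule or contraception period changes.

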3 STUDY OBJECTIVES

3.1 Primary Objective

The primary objective is to assess the safety and tolerability of up to 3 consecutive daily doses of 1 g *Euphorbia kansui* extract powder prepared as tea in HIV-infected ART-suppressed participants.

3.2 Secondary Objectives

The secondary objective is to determine whether 1 g of *Euphorbia kansui* extract powder prepared as tea, administered up to 3 consecutive daily doses, induces a biologic effect,

measured as immune activation (expression of CD69, CD38, and/or HLA-DR) in CD4+ and CD8+ T cells.

A third objective is to determine whether 1 g of *Euphorbia kansui* extract powder prepared as tea, administered up to 3 consecutive daily doses, reactivates latent HIV, measured as cell-associated HIV RNA and plasma HIV RNA levels.

4 STUDY DESIGN

4.1 Study Overview

Prior trials evaluating latent reactivating agents have demonstrated that a “priming” period appears to yield greater latency reversal.^{5,7} Therefore, we will perform this multi-center, phase I clinical study of kansui in eight HIV-infected ART-suppressed participants as a dose escalation trial with a double-blinded, randomized, placebo-controlled crossover cohort. The first two participants will complete a kansui-only treatment phase in which they will be given a single, open label 1g dose of *Euphorbia kansui* extract powder prepared as tea. The second group of six participants will complete the study twice (once on a decaffeinated black tea placebo treatment arm and once with the kansui treatment arm) in a randomized, double-blinded, placebo-controlled crossover design. Which treatment arm occurs first will be randomly assigned and will include a 56-day washout period between the two phases. A second screening visit will occur immediately following the washout period on Day 88. The second screening visit will occur 14-days prior to starting the second treatment assignment on Day 102; the second treatment phase will therefore begin on Day 88 and end on Day 101 (See Study Events Table). As indicated by the dose-escalation design of the study, participants in the kansui treatment phase for group 2 will receive 3 consecutive daily 1g doses of *Euphorbia kansui* extract powder served as tea.

We propose using a crossover double-blinded design due to our experience in performing *in vivo* studies of latent HIV reactivation. We have previously demonstrated statistically significant inter-individual differences in baseline values of the virologic and immunologic outcomes proposed in our study.² For these reasons, we have applied a similar crossover study design in another recent study which allowed the ability to detect even small differences in HIV RNA levels after intervention.³⁵ Therefore, due to the small detectable changes that most HIV latent reactivating agents (LRAs) produce at the doses tested in these trials^{2,5,36,37} and the possibility of small detected changes from our trial of *kansui*, a within-subject control component to the study will allow us the greatest ability to accurately detect treatment-related differences in our study outcome measures.³⁸

Subjects will initiate dosing on separate days. All safety data from each cohort (through week two of observation) will be collated and presented to an SMC before we escalate to the next dose level, as described below. We hypothesize that 1 g of kansui powdered, measured and prepared as tea, given as a single or 3 consecutive daily doses will be safe and well tolerated. We also hypothesize that kansui given as a single or 3 consecutive daily doses may induce T cell activation (CD69, CD38, and/or HLA-DR expression on CD4+ and CD8+ T cells) and latent HIV reactivation (cell-associated HIV RNA and plasma HIV RNA).

Participants will be screened for eligibility. Individuals meeting inclusion criteria without meeting exclusion criteria will be enrolled in the study in sequential dosing cohorts as below. The following treatment regimens will be used:

- Cohort 1: Kansui Phase of (1 g) x 1 dose (the first N = 2 participants)
- Cohort 2: Kansui Phase of (1 g) x 3 consecutive daily doses that is either preceded or followed by a Placebo Phase (the final N = 6 participants)

Study participants will be followed for 31 days following each treatment phase. There will also be a 56-day washout period in between the two treatment phases. The total duration of the study is expected to be up to 45 days for Cohort 1 and up to 146 days for Cohort 2 (See Study Events Table).

5 CRITERIA FOR EVALUATION

5.1 Primary Efficacy Endpoint

There is not a primary efficacy endpoint aim for this phase I safety and tolerability feasibility study, though we will be reporting changes in measures of T cell activation and latent HIV.

5.2 Safety Evaluations

Incidence and nature of adverse events

5.3 Other Evaluations (include only if applicable)

PBMCs will be collected and stored for future gene expression analyses. Plasma samples will be stored for future PK analyses

6 PARTICIPANT SELECTION

6.1 Study Population

We will perform a dose-escalation, proof-of-concept study of *Euphorbia kansui* extract powder prepared as tea in chronically HIV-infected individuals with long-term ART suppression. A total of 8 ART-suppressed patients will be recruited from the University of Utah for participation in this trial. The University of Utah Principle Investigator will oversee the recruitment of potential participants who meet inclusion criteria. [name] will identify and recruit potential participants through his own clinic panel in Clinic 1A and through a cohort of patients already participating in an ongoing study at the University of Utah entitled, “Analysis of Latent HIV-1 Infection in Peripheral Blood Lymphocytes of Aviremic HIV-1 Infected Patients and Explorations of Therapeutic Misconception.”

Participants will include HIV-positive adults \geq 18 years old with long-term virologic suppression on stable ART, with a plasma HIV RNA below the assay limit of detection, CD4+ cell count >350 cells/mm³, and adequate organ function (per criteria listed below).

6.2 Inclusion Criteria

1. Confirmed HIV-1 infection in adults aged 18 years or older.
2. Continuous therapy with a DHHS recommended/alternative combination ART for least 36 months (at least 3 agents) at study entry with no regimen changes in the preceding 24 weeks.
3. Maintenance of undetectable plasma HIV-1 RNA (<40 copies/ml) for at least 36 months. Episodes of single HIV plasma RNA 50-500 copies/ml will not exclude participation if subsequent HIV plasma RNA is <40 copies/ml.
4. Two CD4+ T cell counts >350 cells/ μ l in the six months prior to screening.
5. Written informed consent obtained from participant and ability for participant to comply with the requirements of the study.

